6.6. Data management

The data management function will be supported by a cloud-based electronic data capture (EDC) system developed by FlaskData.IO (Modi'in, Israel). FlaskData.IO provides services for collection and remote monitoring of clinical trials data, compliant with HIPAA and 21 CFR Part 11. EDC portals with secure authorized access will be made available to every participating site, as well as to the study monitor.

Data captured by the clinical personnel will be entered directly into pre-specified eCRF screens by the site personnel. Data from paper sources will be entered into the study database. Automatic data checks will be implemented for majority of entry fields to provide opportunity for resolving data inconsistencies as soon as possible to its occurrence. Efforts will be made to identify missing or incorrect data and promptly resolve these issues.

Data collected by the smartphone application will be directed to a secured cloud-based database where it will undergo analysis aimed at detecting of missing data and other inconsistencies. The smartphone will transmit PRO and technical data containing activation times, stimulation intensity and ePRO via the smartphone to a central electronic database for analysis. Activities such as repeatedly aborted programs, missing feedbacks, inconsistent stimulation intensity adjustments, will be communicated to the research coordinator of the corresponding site, using the participants' ID codes. Automated means were developed to identify and provide corresponding notifications regarding events that

Nerivio TCH-004 Clinical Study Protocol (NCT04089761)

Doc ID: TEC0105

Revision #: 1.0

Page: 33 of 49

may lead to protocol deviations and/or missing data, and which resolution may require involvement of study personnel. Examples of such events include missing PRO data or low device battery level. An automated system was implemented to notify the participant, site study coordinator and the sponsor's study monitor of such issues. Missing data will be automatically identified by a script running on the cloud of FlaskData.IO, and queries will be generated to the participants and the corresponding site study coordinator. Near real time detection of problems in accumulating data will allow timely generation and resolution of queries. Intermediate data processing and translation into eCRF format will be performed. Processed data are further pushed into the EDC system.

A daily back-up of the database will be performed. In addition, a copy of each participant's ePROs and other activities will be stored in his/her smartphone memory and can be retrieved if needed.

EDC tools will be used for locking the database and exporting to SAS compatible format for interim and final statistical analyses. Query resolution will also be performed using EDC tools.

All paper-based source data and relevant medical documents that also serve as source documents will be maintained by the sites and will be available as eCRF attachments. participant identification will be removed from all data and the participants will be identified by their codes. The site investigator is responsible for ensuring that eCRFs are filled in a timely manner and that relevant paper documents are properly stored. The investigators will provide the documents to the sponsor either through the sponsor representative or by mail per the sponsor's request.

Access to data will be authorized and controlled, in accordance with relevant regulations and guidelines.

The study will be performed according to the protocol. At each site, the PI will appoint staff member(s) that will be responsible for completing the CRFs supplied by the sponsor. Specifics of data query handling are given in data management and monitoring plans. Audit trail for data entry and corrections will be maintained.

6.7. Monitoring plan

An independent data monitoring committee (DMC) will be responsible for providing oversight of the data monitoring issues. The DMC will periodically review and evaluate the accumulated data. The DMC will make recommendations regarding enrollment, continuation, modification, or termination of the study. The data reviewed by the DMC will include a summary of the following topics:

- Study progress: subject recruitment, comparison with recruitment targets, retention, protocol adherence, and quality of data collection procedures
- Treatment monitoring: data on treatment integrity and adherence

Nerivio TCH-004 Clinical Study Protocol (NCT04089761)

Doc ID: TEC0105

Revision #: 1.0 Page: 34 of 49

• Safety monitoring: data related to the safety of the subjects, including any device-related adverse events or side effects related to the treatment

7. Statistical Considerations

7.1. Study design and aim

The study is designed as a prospective, open label, multicenter clinical trial. This study aims is to evaluate the safety and efficacy of Nerivio[™] for the acute treatment of migraine with or without aura in adolescents (ages 12-17 years).

7.2. Endpoints

7.2.1. Primary endpoints

The primary endpoints of the study are related to the safety of the device. Safety and tolerability will be assessed by review of all safety parameters, including adverse events. The incidence of adverse events will be assessed as a function of severity and association to the device. The time of resolution of the adverse events and need for treatment will also be analyzed.

7.2.2. Secondary endpoints

Secondary efficacy endpoints include:

- Proportion of subjects reporting, for the test treatment, pain relief at 2 hours post treatment without use of rescue medication. Pain relief is defined as an improvement from severe or moderate pain to mild or no pain, or from mild pain to no pain.
- Proportion of subjects reporting, for the test treatment, pain-free at 2 hours post treatment without use of rescue medication. Pain free is defined as an improvement from mild, moderate or severe pain to no pain.
- Proportion of subjects reporting, for the test treatment, nausea at baseline and achieving absence of nausea at 2 hours post treatment without use of rescue medication.
- Proportion of subjects reporting, for the test treatment, phonophobia at baseline and achieving absence of phonophobia at 2 hours post treatment without use of rescue medication.
- Proportion of subjects reporting, for the test treatment, photophobia at baseline and achieving absence of photophobia at 2 hours post treatment without use of rescue medication.

Nerivio TCH-004 Clinical Study Protocol (NCT04089761)

Doc ID: TEC0105

Revision #: 1.0 Page: 35 of 49

7.2.3. Exploratory endpoints

Exploratory efficacy endpoints include:

- Proportion of subjects achieving, for the test treatment, pain relief at 2 hours post treatment without use of rescue medication and no relapse of headache pain within 24 hours.
- Proportion of subjects achieving, for the test treatment, pain freedom at 2 hours post treatment without use of rescue medication and no relapse of headache pain within 24 hours.
- Proportion of subjects achieving, for the test treatment, improvement of at least one grade in functional disability at 2 hours post treatment without use of rescue medication.
- Proportion of subjects achieving, for the test treatment, improvement of at least one grade in functional disability at 24 hours post treatment without use of rescue medication.

7.3. Sample size

A sample size was calculated on the efficacy endpoint of pain relief at 2 hours post-treatment. Calculations show that a sample size of 110 participants would provide 80% power to determine that 60% ($\pm 6\%$) of the participants will achieve pain relief at 2 hours post-treatment. The sample size may be increased to up to 130 participants to account for a potential ~15% drop-out rate and/or missing data.

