7.5. Statistical analysis

7.5.1. General considerations

Statistical analyses will be performed using SAS® v9.4 or higher (SAS Institute, Cary NC, USA).

Baseline demographic and other baseline characteristics, together with safety analyses will be performed on all participants who underwent the treatment phase. Baseline values are defined as the last valid value prior to treatment.

Where confidence limits are appropriate, a two-sided 95% confidence interval will be constructed.

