7.5.4. Efficacy analysis

The efficacy endpoints will be assessed on evaluable treatments of qualifying attacks. The first use of the device is considered a training treatment and will not be included in the efficacy analyses. The first treatment of a qualifying attack after the training treatment is considered a test treatment and will be used for all efficacy assessments. If this treatment is not evaluable (i.e., no pain data at 2 hours post-treatment), a subsequent treatment of a qualifying attack with evaluable data will be considered the test treatment.

Use of rescue medication before the 2-hours assessment will be considered a treatment failure for the 2-hours endpoints, and before the 24 hours assessment for the sustained

Nerivio TCH-004 Clinical Study Protocol (NCT04089761)

Doc ID: TEC0105

Revision #: 1.0

Page: 37 of 49

24-hours endpoints. The percentage of participants achieving each of the efficacy outcomes will be presented in a tabular form along with two-sided 95% exact confidence intervals.

For the associated symptoms outcomes, the observed response proportions and corresponding 95% exact confidence intervals for each associated symptom will be provided. All patients with baseline and 2 hours values will be included in the analyses. A response in each associated symptom (nausea, vomiting, photophobia, phonophobia) is defined as change from presence of a specific associated symptom at baseline to absence of the same associated symptom at 2 hours post-treatment.

In addition, logistic regression models will be used to assess the efficacy. Baseline value and site will serve as covariates.

The first secondary endpoint (pain relief at 2 hours) may also be evaluated in attacks with aura and attacks without aura separately.

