9.1. Protocol amendments

The protocol cannot be amended by the investigator without obtaining the sponsor's approval. Protocol amendments will be submitted for approval to local IRB/EC and, if applicable, to the respective regulatory authority (RA). The amendments can be implemented in the study only after an IRB/EC and/or RA approval are obtained. Non-substantial changes (e.g. minor logistical or administrative changes, change of monitor(s), telephone numbers, renewal of insurance) which do not affect the rights, safety and well-being of human subjects and/or are not related to the clinical investigation objectives or endpoints, may only require a notification to the IRB/EC and/or regulatory without protocol amendment.

The following documents are relevant to the protocol but are not considered part of the protocol. These documents are stored and modified separately. As such, modifications to these documents do not require protocol amendments:

- Site roster
- Case report forms
- Data management plan
- Monitoring plan
- Statistical analysis plan
- DMC

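### Section 7.3 claims 80% power for a 60% (±6%) pain relief rate with 110 participants but names no null rate, alpha or test; the planned 95% exact interval is about ±9.5 points

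*Combined protocol and SAP*

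**What the plan says.** Section 7.3 bases the sample size on pain relief at 2 hours. It states: "Calculations show that a sample size of 110 participants would provide 80% power to determine that 60" per cent, with ±6% in brackets, achieve pain relief. It then allows an increase to 130 for about 15% drop-out or missing data. It gives no formula, null rate, alpha or test.

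The analysis sections do not supply them:

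- Section 7.5.1: "Where confidence limits are appropriate, a two-sided 95% confidence interval will be constructed".
- Section 7.5.4 reports the percentage achieving each efficacy outcome "along with two-sided 95% exact confidence intervals". It continues: "In addition, logistic regression models will be used to assess the efficacy", with baseline value and site as covariates and no reference rate.
- Section 5.2 states the hypothesis in words only, and the design is single arm, so no comparator provides a null.
- Section 7.2.1: "The primary endpoints of the study are related to the safety of the device". Pain relief is the first secondary endpoint.
- Section 9.1 names a statistical analysis plan among documents stored separately: "The following documents are relevant to the protocol but are not considered part of the protocol". Section 7.3 does not refer to it.

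**The concern.** Power is the probability that a specified test rejects a specified null at a specified alpha. Section 7.3 gives a power figure without any of the three, and attaches a ±6% that reads like the half-width of an interval. The two ideas appear to have been mixed.

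This sentence is the only quantitative justification of the trial's size in the supplied documents. A reader will take from it either that the study can distinguish 60% from a rate 6 points away with 80% power, or that the rate will be estimated to within 6 points. The first fails at any conventional alpha. The second does not describe the 95% interval that will be reported.

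**Working it through.** **Inputs.** n = 110, 80%, 60% and ±6 points (7.3); two-sided 95% exact intervals (7.5.1, 7.5.4); about 15% drop-out (7.3). Null rate, alpha and test are not stated, so the test calculations below run over a range of assumed values.

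**1. Reproducing 110.** The Wald half-width formula is n = z² × p(1 − p) / d², with p = 0.60 and d = 0.06.

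| Two-sided confidence | z | n for ±6 points |
|---|---|---|
| 80% | 1.2816 | 1.2816² × 0.24 / 0.0036 = 109.5 |
| 90% | 1.645 | 180.4 |
| 95% | 1.960 | 256.1 |

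The 80% row rounds up to 110 and uses all three stated inputs (80%, 60%, 6 points). Equivalently, if the true rate is 60%, the probability that the observed rate lies within 6 points of it (60 to 72 responders of 110) is 0.794. The drop-out step also reproduces: 110 / 0.85 = 129.4, rounded up to 130.

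**2. Testing the power claim with 6 points as the margin.** Exact one-sided binomial test, n = 110. The critical value is the smallest responder count whose upper-tail probability under the null is at or below alpha.

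| One-sided alpha | 60% vs null 54%: critical value, power | 66% vs null 60%: critical value, power |
|---|---|---|
| 2.5% | 71, 19% | 77, 22% |
| 5% | 69, 32% | 75, 35% |
| 10% | 67, 46% | 74, 43% |
| 20% | 65, 62% | 71, 67% |

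For 60% against 54%, power first reaches 80% at a critical value of 62 (power 81%), where the one-sided alpha is 34%.

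**3. What null would give 80% power?** At one-sided 2.5% with a true rate of 60%, a null of 46% gives 81% (critical value 62) and a null of 47% gives 75% (critical value 63). The margin needed is therefore about 60 − 46 = 14 points, and 7.3 names no such null.

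**4. Another route to 110.** A test of 60% against 50% at one-sided 10% with 80% power gives, by the normal approximation, (1.2816 × 0.5 + 0.8416 × 0.4899)² / 0.10² = 110.9. Its exact power at n = 110 is 75%. It does not use ±6%, and neither its null nor its alpha is in the documents.

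**5. Precision of the planned analysis.** Clopper-Pearson intervals at an observed 60%:

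| Responders | Confidence | Interval | Half-width |
|---|---|---|---|
| 66/110 | 95% | 50.2% to 69.2% | 9.5 points |
| 66/110 | 80% | 53.5% to 66.3% | 6.4 points |
| 78/130 | 95% | 51.0% to 68.5% | 8.7 points |

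Even if all 130 were evaluable, the 95% half-width would exceed 6 points. Reaching ±6 points at 95% confidence takes about 257 participants (Wald) or 271 (exact).

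**The case against.** The strongest defence is that the sentence is nearly true if read differently: with a true rate of 60%, there is a 79.4% chance that the estimate falls within 6 points of it. On that reading 110 is correctly calculated, only the word power is wrong, and an 80% chance of being close does not conflict with a 95% half-width of 9.5 points, because they are different quantities. The 19% figure then answers a test that the protocol never proposed. The consequence is also small: the endpoint is secondary and has no success threshold, and the 95% exact interval is prespecified, so the report will show the true uncertainty. Finally, the separate statistical analysis plan may hold the missing inputs.

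Much of this stands. The number 110 is not itself miscalculated if precision at 80% confidence was meant, and the power figures apply only if 6 points is the test margin. But the 79.4% reading is the same 80% confidence calculation in another form, and it concedes that power is the wrong term. It also leaves 7.3 using an 80% level where 7.5.1 and 7.5.4 use 95%. The separate plan could supply a null and an alpha, but it cannot make ±6 points the half-width of a 95% exact interval at 60% with n = 110. The limited consequence bears on severity, not on whether the statement is right.

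**Conclusion.** The concern holds. As written, 7.3 claims a power that the supplied text gives no means to derive and that a 6-point margin does not yield: 19% at one-sided 2.5% and 62% at one-sided 20% for 60% against 54%. The precision a reader would infer is also too favourable. The planned 95% exact interval at 60% is about ±9.5 points, with a lower limit near 50% rather than 54%.

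That 110 came from an 80% confidence calculation is an inference. It fits all three stated inputs, but no formula is shown, the exact 80% half-width is 6.4 points, and the test in step 4 also lands near 110. The finding does not depend on the origin.

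The interval figures assume 110 evaluable participants and an observed rate of 60%. Nothing is claimed about how many of the 130 will be evaluable, because the documents do not settle whether 130 counts enrolled or treated participants. This should be fixed, but it does not affect the primary safety and tolerability endpoints or invalidate the planned efficacy analysis.

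**What to change.** Do one of two things in 7.3.

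- **A. If no test is intended:** delete the 80% power claim and the ±6%, and state the precision of the planned analysis. Suggested wording: *With 110 evaluable participants and an observed rate of 60%, the two-sided 95% exact confidence interval is 50.2% to 69.2% (half-width about 9.5 points).*
- **B. If a test was intended:** state its null rate, alpha, sidedness and method, and the power it gives at n = 110, and add that test to 7.5.4.

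Option A matches the analysis already planned. It costs one sentence in 7.3, adds no participants and changes no analysis; the only price is a less favourable stated precision. Option B costs wording in 7.3 and one added test in 7.5.4.

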7.4. Analysis sets

Intent to treat analysis set (ITT)

The ITT analysis set includes all patients undergoing the treatment phase.

Modified intend to treat analysis set (mITT)

The mITT analysis set includes all patients undergoing the treatment phase and treat a test treatment within 60 minutes of attack onset. Subjects with no valid post baseline assessment will not be included in the relevant analysis.

Per-protocol analysis set (PP)

The PP analysis set includes all patients from the mITT analysis set without major protocol deviations. Main protocol instructions include:

- has started within 60 minutes of attack onset
- was administered to treat a qualifying migraine attack
- was administered for at least 30 minutes
- includes data on pain intensity at 2 hours post-treatment
- rescue medication was not used before or within 2 hours post-treatment

Nerivio TCH-004 Clinical Study Protocol (NCT04089761)

Doc ID: TEC0105

Revision #: 1.0

Page: 36 of 49

Statistical analysis of the analysis sets

The ITT analysis set will serve as the main set for safety assessments.

The mITT analysis set will serve as the primary set for the efficacy assessment.

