	III. Disappearance of photophobia in the test treatment at 2 hours post-treatment			
Exploratory	Sustained pain relief at 24 hours post-treatment:			
endpoints	The proportion of participants achieving pain relief at 2 hours post-			
	treatment in the test treatment, with no use of rescue medication and no			
	relapse of headache pain within 24 hours			
	2. Sustained pain-free at 24 hours post-treatment:			
	The proportion of participants achieving pain freedom at 2 hours post-			
	treatment in the test treatment, with no use of rescue medication and no			
	relapse of headache pain within 24 hours			
	Functional disability at 2 hours post-treatment			
	The proportion of participants achieving improvement of at least one			
	grade in functional disability in the test treatment at 2 hours post-			
	treatment with no use of rescue medication			
	Functional disability at 24 hours post-treatment			
	The proportion of participants achieving improvement of at least one			
	grade in functional disability in the test treatment at 24 hours post-			
	treatment with no use of rescue medication			
Datasets	Intent to treat analysis set (ITT)			
	The ITT analysis set includes all participants undergoing the treatment			
	phase.			
	Modified intent to treat analysis set (mITT)			
	The mITT analysis set includes all participants undergoing the			
	treatment phase who treat a test treatment within 60 minutes of attack			
	onset.			
Data Analysis	The ITT analysis set will be used for the primary endpoints of safety and			
	tolerability assessments. Safety assessments will include spontaneously			
	reported adverse events. The mITT analysis set will be used for the efficacy			
	assessments.			

Nerivio TCH-004 Clinical Study Protocol (NCT04089761)

Doc ID: TEC0105

Revision #: 1.0

Page: 11 of 49

2. Background

Migraine is one of the most prevalent and disabling neurologic disorders [1], characterized by recurrent headache attacks with nausea, vomiting, photophobia, and phonophobia [2]. Migraine is also common in adolescents (12 to 17 years of age) [3]. Migraine in adolescents has also been associated with disability as evidenced by missed school days [4], poorer performance in school [5] and a negative impact on quality of life [6].

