The primary efficacy endpoint was the proportion of participants who achieved pain relief at 2 hours post-treatment in the "test treatment", defined as improvement from severe or moderate pain to mild or none, or, improvement from mild pain to none. The secondary efficacy endpoints pain-free (improvement from mild, moderate, or severe pain to none), MBS relief, pain relief & MBS relief, and MBS freedom at 2 hours post-treatment. Exploratory endpoints included 48-hour sustained pain-free and pain relief responses. An additional exploratory endpoint was within-subject consistency, defined as the proportion of participants achieving pain relief at 2 hours post-treatment in at least 50% of their treated attacks. Pain relief at 2 hours post-treatment as function of baseline pain level was also explored.

Results

296 participants were enrolled; 252 were randomized after the "run-in" phase, 126 were assigned to the active group and 126 to the sham group. Of the 44 who were not randomized, 33 failed to meet the "roll-in" criteria, 9 withdrew from the study and 2 were

Nerivio TCH-004 Clinical Study Protocol (NCT04089761)

Doc ID: TEC0105

Revision #: 1.0

Page: 21 of 49

withdrawn by the investigator due to migraine misdiagnosis. Among the 252 randomized participants (intent-to-treat population), 7 withdrew from the study, 3 (1 sham, 2 active) due to intolerance to the stimulation and 4 (2 sham, 2 active) were lost to follow up. 237 participants completed at least one treatment (the "run-in" treatment) and 203 participants completed the "test treatment". 202 participants (99 in the active group and 103 in the sham group) started the "test treatment" within one hour from symptom onset and reported pain level at 2 hours, forming the mITT population with evaluable data. 37 participants who did not complete the "test treatment", due to insufficient migraine attacks (n=18), participant's decision not to use the device (n=4), other (n=6) or unknown (n=9), were excluded from the efficacy analyses.

The demographic and clinical characteristics were similar between treatment groups (Table 4). The characteristics of treated migraine headaches were comparable to those reported in previous migraine studies [23–25].

Table 4: Demographic and clinical characteristics (intent-to-treat population)

Characteristic	Active group (n=126)	Sham group (n=126)	
Age, y (SD)	43.8 (12.25)	41.6 (11.81)	
Female, % (n/N)	80.9% (102/126)	80.9% (102/126)	

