6.3. Procedures

This open label study includes 3 phases and up to 4 visits. All visits will be conducted in the presence of a parent/guardian.

First visit – enrollment: The first visit will include screening, enrollment and training on the application in diary mode. The screening process will include an eligibility assessment and a urine pregnancy test. Following successful screening, enrollment interview and signing an informed consent by the parent/guardian and an informed assent by the participant. The participants will be trained to use the electronic diary application, installed on their own smartphones. The site personnel will be required to document the training session in the CRF. During this visit, participants will complete baseline questionnaires that included information on the frequency and severity of their migraine attacks, typical associated symptoms, use of preventive and acute treatments, and the effect that their migraine attacks have on their daily routine and quality of life.

Nerivio TCH-004 Clinical Study Protocol (NCT04089761)

Doc ID: TEC0105

Revision #: 1.0

Page: 29 of 49

Phase 1 – run-in phase: After the enrollment visit, participants will undergo a 4-week migraine diary phase aimed to collect baseline migraine characteristics and further assess eligibility. Participants will be asked to report in the application each migraine attack. These reports will be transferred by the application to the electronic data collection (EDC) system, where they will be collected and registered. Participants who did not have at least 3 migraine attacks will be excluded from the study. Eligibility will also be determined based on the compliance of participants to report the attacks within one hour from attack onset and report the pain level at 2 hours post-treatment in at least 66.7% of the reported attacks.

Second visit – **Device training visit:** Eligible participants who meet the run-in requirements will receive the Nerivio[™] device. The device will be registered and connected by Bluetooth to their smartphone. During this visit, participants and their parent/guardian will be trained to use the device, including finding the optimal individual stimulation intensity level (perceptible but not painful). The site will also carefully review with the patient and parent/caregiver how to identify a qualifying migraine attack (see below) and provide detailed instructions on study procedures.

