The individual intensity level identified during this visit will be recorded, and the participants will be asked to treat their migraine headaches with the device using the identified intensity. If the research staff recognizes that the participant cannot tolerate the feeling of the electrical stimulation, the participant may be withdrawn from the study.

During the training, participants will also be informed on the key elements which are critical for the successful conduct of the study:

- Treatments of attacks with Nerivio[™] should be performed as soon as possible
 after migraine headache or aura began and always within one hour of symptoms
 onset. Treatments of mild headaches are accepted.
- Avoid taking rescue medications within two hours post-treatment (2 hours from start of treatment), if possible.
- The treatment should be performed for at least 30 minutes (the recommended treatment duration is 45 minutes).

Phase 2 –Treatment phase: Participants will be instructed to use the device for the treatment of 4 qualifying migraine attacks (see below) as soon as possible and always within 60 minutes of onset during a period of up to 8 weeks. Participants will be instructed to use the device with the intensity level identified during the device training visit (with a range of ±5 units) and make sure the stimulation is perceptible but not painful. Participants will be instructed to avoid taking rescue medications within 2 hours post-treatment. If medications are used, participants will be instructed to record in the app when and which medication was taken. The participants will use the app to record pain intensity levels (none, mild, moderate, or severe) at baseline, 2- and 24-hours post-treatment, and to record the presence/absence of associated migraine symptoms (nausea, photophobia,

Nerivio TCH-004 Clinical Study Protocol (NCT04089761)

Doc ID: TEC0105

Revision #: 1.0

Page: 30 of 49

phonophobia) at baseline and 2 hours post-treatment. To assess functional disability, participants will also record at baseline, 2- and 24-hours post-treatment their response to the following question in their diary: "How do you rate your ability to do school-work or perform your usual activities?" using a 4-point scale ('as usual', 'some ability', 'a little ability', 'no ability at all'). At the beginning of each treatment, participants will also be asked to report the time elapsed from attack onset. Adverse events will be reported throughout this phase of the study.

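### As 6.3, 7.4 and 7.5.1 most naturally read, the set for both primary endpoints omits participants stimulated and withdrawn for intolerance at visit 2; the synopsis allows the opposite reading, so the sections must be reconciled

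*Combined protocol and SAP*

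**What the plan says.** **The set.** Section 7.4: "The ITT analysis set includes all patients undergoing the treatment phase", and "The ITT analysis set will serve as the main set for safety assessments". The synopsis (Data Analysis) gives it the same role: "The ITT analysis set will be used for the primary endpoints of safety and" tolerability. Section 7.5.1 repeats the limit: "safety analyses will be performed on all participants who underwent the treatment phase". No set based on first exposure to the device is defined.

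**The sequence.** Section 6.3 describes the run-in (Phase 1), then the second visit (device training), then Phase 2 (treatment). At the second visit the device is connected and the individual stimulation level is found. If staff see that a participant "cannot tolerate the feeling of the electrical stimulation, the participant may be withdrawn from the study". That sentence comes before the Phase 2 text.

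**Adverse events.** Within the Phase 2 text, 6.3 says: "Adverse events will be reported throughout this phase of the study". Section 12.2 is broader: it has every adverse event recorded and used in the safety assessment, with no limit by phase.

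**The endpoints (6.4.1).** One is the incidence of adverse events. The other is the percentage of participants who do not complete the study because of adverse events. Section 7.5.3 adds Kaplan-Meier curves of time to withdrawal without stating a time origin.

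**The concern.** The trial's primary question is whether a new age group tolerates the device. First exposure happens at visit 2, and the same visit offers an exit for those who cannot tolerate it. If the safety set opens only after that exit, the participants least able to tolerate stimulation are screened out between first exposure and the start of counting. Both primary endpoints would then describe a group already selected for tolerance.

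Comparison with the adult pivotal study would suffer too. In 4.2.2, device training took place at the randomisation visit and the ITT population was all 252 randomised. It therefore kept the three participants who withdrew "due to intolerance to the stimulation".

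**Working it through.** **Step 1. Does the set include visit 2?** The sections side by side:

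- *Against inclusion:* 6.3 treats the second visit as a separate item placed between Phase 1 and Phase 2. Sections 7.4 and 7.5.1 both require that the participant underwent the treatment phase. Someone withdrawn at visit 2 has treated no attack.
- *For inclusion:* the synopsis says that those meeting the run-in requirement are included in the treatment phase, and it opens Phase II with receipt of the device, which 6.3 places at visit 2. Section 7.5.4 calls the first use of the device the training treatment, and 6.3 puts the training treatment in the safety analysis (although 6.3 defines it as the first reported treatment).

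The start of the treatment phase is not defined, nor is what counts as undergoing it. Exclusion is the more natural reading of 6.3, 7.4 and 7.5.1 together, but it is not the only one.

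**Step 2. Inputs for size.** The plan states no figure for the safety or tolerability endpoints. Section 7.3 sizes the trial on pain relief: 110, raised to 130 for about 15% dropout. This reproduces: 110 / (1 − 0.15) = 129.4, rounded up to 130. I take 130 as the number stimulated at visit 2. The number k withdrawn there is an assumption. Section 7.5.1 asks for two-sided 95% intervals; I use exact (Clopper-Pearson) limits:

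- zero events in n: upper limit = 1 − 0.025^(1/n)
- x > 0 events in n: lower = 2.5% quantile of Beta(x, n − x + 1); upper = 97.5% quantile of Beta(x + 1, n − x)

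**Step 3. Change the set only.** Take k = 2, no later withdrawals, and intolerance not classed as an adverse-event withdrawal:

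- as written: 0/128, upper limit 1 − 0.025^(1/128) = 2.84%
- all stimulated: 0/130, upper limit 1 − 0.025^(1/130) = 2.80%

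The denominator effect is negligible.

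**Step 4. Change the set and count intolerance as failure.** No later withdrawals:

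| k at visit 2 | As written | All stimulated |
|---|---|---|
| 1 | 0/129 = 0% (0 to 2.8%) | 1/130 = 0.8% (0.0 to 4.2%) |
| 2 | 0/128 = 0% (0 to 2.8%) | 2/130 = 1.5% (0.2 to 5.4%) |
| 3 | 0/127 = 0% (0 to 2.9%) | 3/130 = 2.3% (0.5 to 6.6%) |
| 5 | 0/125 = 0% (0 to 2.9%) | 5/130 = 3.8% (1.3 to 8.7%) |

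With k = 2 and two later adverse-event withdrawals: 2/128 = 1.6% (0.2 to 5.5%) against 4/130 = 3.1% (0.8 to 7.7%). With 110 stimulated, k = 2 and none later: 0/108 (upper limit 3.4%) against 2/110 = 1.8% (0.2 to 6.4%).

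**Step 5. The adverse-event endpoint.** Here the set matters however intolerance is classified. Each participant who has an adverse event at visit 2 and is withdrawn there adds 1/130 = 0.8 percentage points once included, and nothing if excluded.

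**The case against.** Four points on the other side deserve weight.

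- **The boundary is open.** A reader might infer that the set definitely starts after visit 2 and that the results are therefore biased toward zero. The synopsis does not support so firm a statement: on its wording, passing the run-in and receiving the device already belong to Phase II. This stands, and it limits the point to a natural reading plus a need to reconcile. It does not remove the point, because the membership of a primary analysis set should not be settled after the data are seen.
- **Adverse events at visit 2 are not lost at source.** A reader might infer from 6.3 that collection begins only in Phase 2. Section 12.2 is not limited by phase, and 3.9 has the training session documented in the CRF and the study database. This stands. An event could still be recorded and then left out of the analysis by 7.5.1.
- **The tolerability figure depends on classification.** A reader might infer that a wider set alone moves the rate from 0% to 1.5%. It does not (step 3). In the adult study three participants left for intolerance, yet 4.2.2 reports no withdrawal due to adverse events. Sections 6.1.4 and 7.5.6 also name intolerance separately from adverse events. This stands, so the fix has two parts.
- **The adult rate is not a visit-2 rate.** Two of 126 active participants (1.6%) withdrew for intolerance, but 4.2.2 does not say when. It cannot serve as a forecast for adolescents at visit 2.

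Section 7.5.3 also reports non-completion for any reason, which might seem to catch these cases. That table falls under the same 7.5.1 restriction, so on the natural reading it would miss them as well. Review of retention by the monitoring committee (6.7) is oversight and does not change the reported endpoint.

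**Conclusion.** The point holds in limited form. On the natural reading of 6.3 with 7.4 and 7.5.1, participants stimulated and withdrawn at visit 2 fall outside the set for both primary endpoints. The synopsis permits the contrary reading, and the plan must say which applies.

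The expected size is small and cannot be estimated from the documents. The shift from 0% (0 to 2.8%) to 1.5% (0.2 to 5.4%) is an illustration. It rests on 130 stimulated, 2 stopping at visit 2, none stopping later, and intolerance counted as failure. Without the last assumption the tolerability rate hardly moves, and the gain from a wider set lies in the adverse-event endpoint and in a complete account of withdrawals. The matter is still worth settling: when a primary endpoint may come out close to zero, one or two participants decide whether the report says none or some.

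**What to change.** - In 7.4 and 7.5.1, define the safety set as every participant who received any device stimulation, including at visit 2, and use it for both primary endpoints. Bring the synopsis and 6.3 into line on when the treatment phase starts. The mITT set for efficacy stays as it is.
- State in 6.3 and 7.5.1 that adverse events recorded from visit 2 onward, which 12.2 already covers, enter the safety analysis.
- In 7.5.3, set time zero of the Kaplan-Meier time to withdrawal at visit 2.
- In 6.4.1 and 7.5.3, report withdrawal for intolerance of the stimulation as a tolerability failure, shown alongside adverse-event withdrawals so that both counts are visible. Without this step the new set leaves the tolerability rate almost unchanged.

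The cost is wording: no new visit or data source is needed, because the training session and the stimulation level found there are already recorded. The downside is a slightly less favourable safety and tolerability figure.
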